13.6 Exploratory Endpoints

For each patient on the study, grip strength will be correlated with AIA score using logistic regression analysis and Spearman correlation at three time points throughout the study – baseline, week 12, and week 52. At five years, we will also compare breast cancer recurrence rates in each arm using Kaplan-Meier survival analysis and log-rank test.

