The significance of the arthralgia syndrome associated with AI therapy is clarified by looking at a small pilot study which prospectively evaluated 100 women on adjuvant AI therapy with serial questionnaires. At a median of six months, 13% of these women discontinued aromatase inhibitor therapy because of arthralgia (10). In larger studies, overall rates of non-adherence to AI therapy for any reason are even higher. From reviewing pharmacy records of 12,000 patients, one researcher found the rate of adherence to adjuvant anastrazole therapy was only 50-68% at three years (20). The joint pains, as they are one of the most common and troubling side effects of AI therapy, most likely play a significant role in patient's non-adherence to medication.

The significance of AIA, however, may extend beyond issues of quality of life and compliance. It is possible that AIA is a marker of increased biologic effect. Retrospective analysis of the ATAC trial suggests that women who develop new joint pains within three months of beginning endocrine therapy (either AI or tamoxifen) have a 40% reduction in the risk of breast cancer recurrence as compared to those women without arthralgia (21), similar to the increased efficacy seen in lung cancer patients who develop a rash with erlotinib. Retrospective analyses of the TEAM

and BIG 1-98 trials have also found a correlation between the development of arthralgia on AI therapy and lower breast cancer recurrence risk, as compared to those who do not develop arthralgia (22) (23). However, it should be noted that analysis of IES did not show the same correlation (24). Clearly, more needs to be learned about the etiology and the significance of AIA. Further study of AIA could potentially lead to a better understanding of factors that predict disease recurrence.

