2.3 Exploratory Objective

- 2.3.1 To study whether grip strength may serve as an accurate and reliable objective measure to complement the subjective complaint of AIA.
- 2.3.2 To investigate whether high dose vitamin D may be associated with lower breast cancer recurrence than standard dose Vitamin D

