3. STUDY DESIGN/SUMMARY

This is a randomized, multi-center, controlled, phase II study comparing high dose vitamin D vs. standard dose vitamin D for post-menopausal breast cancer patients who are beginning adjuvant aromatase inhibitor therapy. The study is intended to be conducted in up to 5 centers within the U.S.A which are routinely engaged in the administration of aromatase inhibitor therapy for the study specified population. All patients who are starting an AI in the adjuvant setting are eligible to participate in the study.

In order to preserve power and compensate for the interim futility analysis which tends to reduce power, the sample size of the study is increased from 88 per group to 93 per group, which is 186 total if considering a 5% drop out rate. A total of 186 patients at up to 5 centers will be randomized 1:1 to receive either 50,000 International Units (IU) oral vitamin D per week for 12 weeks followed by 2000 IU daily for 40 weeks, or 800 IU Vitamin D daily for 52 weeks. All women on both arms of the trial will also take calcium carbonate 600 mg daily.

The primary endpoint for this study is development of AIA in each arm after 12 weeks of AI therapy, as determined by patient questionnaires. Secondary endpoints include compliance with AI therapy, as well as correlation of low baseline vitamin D levels with development of AIA. Grip strength is an exploratory endpoint.

[figure not shown]
Throughout the 52 week study period, participating women will complete the questionnaire and grip strength measurement a total of three times in order to assess their arthralgia while on AI therapy. Compliance with aromatase inhibitor (AI) therapy will also be assessed throughout the

Vitamin D for AIA

study to determine if AI compliance is improved in women who are receiving Vitamin D. Additionally, women will also have periodic assessments of serum 25-hydroxyvitamin D to assess whether vitamin D levels correlate with AIA, and to ensure that calcium and 25(OH) D levels are within healthy ranges.

SCHEMA

High Dose vs. Standard Dose Vitamin D for Aromatase Inhibitor-Induced Arthralgia

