13.2 Sample Size/Accrual Rate

The primary objective of this study is to determine if supplementation of high dose Vitamin D prevents AIA in women being treated with adjuvant aromatase inhibitors. The Health Assessment Questionnaire II (HAQ-II) will be used to assess joint pain symptoms. Previously published estimates of AIA incidence showed that 33% of women on standard dose of vitamin D, and 19% of women on a high dose of vitamin D, developed AIA (43). Assuming a one-sided test with $\alpha=0.10$, $\beta=0.20$, we would need 93 women in each arm to detect a different rate of AIA development using the Chi-square test. Assuming 5% dropout rate in the first 12 weeks, we will accrue 93 women to each arm, for a total of 186 women. Sample size calculations were conducted using nQuery Advisor 7.0, Statistical Solutions, USA. Given that there are over 8000 office visits each year in our Baylor Clinic and Smith Clinic, we should easily be able to recruit an average of 4-6 women/month to the study, which would allow us to complete accrual in approximately 3 years.

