13.4 Primary Endpoint

Descriptive and summary statistics will be computed for all demographic and clinical data in each treatment group. The HAQ-II will be used to assess joint pain symptoms; a higher score indicates more severe joint pain. Scores will be evaluated for the development of AIA between baseline and Week 12, as well as between baseline and Week 52, though development of AIA at 12 weeks will be the primary endpoint. The scores will be dichotomized as “development of AIA” (as defined above, in Section 12.2) or “no development of AIA.” Group differences in AIA rate will be assessed using the Chi-square test. Development of AIA at week 12 will be used to test the primary objective. The week 52 data will be measured and reported as well. As exploratory analyses, development of AIA will be assessed using logistic regression, adjusting for potential confounders such as age at diagnosis, race/ethnicity, BMI, receipt of chemotherapy, taxane use, and use of hormone replacement therapy. All statistical tests are one-sided with $\alpha = 0.10$ as the level of significance.

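### Read literally, the blanket one-sided 0.10 rule leaves the five-year recurrence comparison unable to declare formally an excess in the high-dose arm

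*Combined protocol and SAP*

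**What the plan says.** Section 13.4 (Primary Endpoint) describes the week-12 chi-square comparison and then exploratory logistic regressions adjusted for several covariates. It closes with "All statistical tests are one-sided with" alpha 0.10 as the significance level. No other section narrows that sentence.

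Section 13.6 (Exploratory Endpoints) plans, at five years, to "compare breast cancer recurrence rates in each arm using Kaplan-Meier survival analysis and log-rank test". It states no sidedness, alpha, effect estimate, confidence interval or expected number of events.

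The only direction given for recurrence is in objective 2.3.2, which asks whether high dose may be associated with "lower breast cancer recurrence than standard dose Vitamin D".

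The background points both ways:

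- Section 1.2 raises arthralgia as a possible marker of biologic effect. It cites a retrospective analysis in which women with new joint pains on endocrine therapy "have a 40% reduction in the risk of breast cancer recurrence as compared to those women without arthralgia". It reports similar correlations in two further trials and none in a fourth.
- Section 1.4 reports that higher baseline vitamin D went with fewer distant recurrences.

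**The concern.** A one-sided 0.10 test suits the directional week-12 hypothesis, and the sample size was built on it. Recurrence is different. The intervention is meant to reduce arthralgia, and the protocol itself says that arthralgia may accompany better cancer control. A comparison whose rejection region lies entirely on the benefit side has no formal way to report the opposite result.

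Nothing else planned fills the gap. Adverse event collection stops 30 days after the last dose (Section 9.1). The Data Review Committee looks at accrual, serious adverse events and cumulative toxicity (Section 14.2). The log-rank test in Section 13.6 is the only between-arm comparison of recurrence in the plan. If it is reported as a bare one-sided p-value, a large value could be read as reassurance when the data remain compatible with a substantial excess.

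A smaller matter comes from the same sentence. Some regression covariates carry no hypothesis, so a one-sided test of them has no defined direction.

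**Working it through.** **1. Is one-sided 0.10 the real basis of the primary design?** Section 13.2 gives the rates ("33% of women on standard dose of vitamin D, and 19% of women on a high dose of vitamin D, developed AIA") and the error rates ("Assuming a one-sided test with $\alpha=0.10$, $\beta=0.20$, we would need 93 women in each arm"). The pooled-variance formula with mean rate 0.26 is

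n = [1.2816·√(2·0.26·0.74) + 0.8416·√(0.33·0.67 + 0.19·0.81)]² / 0.14² = (0.795 + 0.515)² / 0.0196 = 87.6, or 88 per group.

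This matches the 88 in Section 13.7, and 88/0.95 = 92.6 gives 93. A two-sided 0.10 design would need 121 per group. The one-sided rule is therefore genuine for the primary comparison, and nothing below alters it.

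**2. What the one-sided test does when high dose has more recurrence.** The documents give no recurrence rate. I assume 5% to 20% at five years. With the 186 women of Sections 3 and 13.2 (Section 13.7 prints 196, which hardly changes the result), that is 9 to 37 events. If the true hazard ratio were 1.5, the test for lower recurrence would reject with probability Φ(−ln(1.5)·√d/2 − 1.2816): 2.9% at 9 events and 0.6% at 37. Those rejections would be in favour of high dose. No outcome leads to a declared excess.

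As an illustration, take 20 events and an observed hazard ratio of 2.0. Then z = ln(2)·√20/2 = 1.55. The one-sided p for benefit is Φ(1.55) = 0.94. The two-sided p is 0.12, with a 95% interval of 2.0/2.40 to 2.0·2.40, or 0.83 to 4.8. The interval shows how much harm remains possible; the one-sided p does not.

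**3. Precision.** The 95% interval extends by a factor exp(1.96·2/√d) on each side of the estimate.

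| Assumed events | Factor each way |
|---|---|
| 10 | 3.5 |
| 20 | 2.4 |
| 30 | 2.0 |

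**4. Power toward harm if the test were two-sided 0.05.** Power = Φ(ln(HR)·√d/2 − 1.96).

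| True HR (assumed) | 9 events | 37 events | Events for 80% power |
|---|---|---|---|
| 1.5 | 9% | 23% | 191 |
| 2.0 | 18% | 56% | 66 |

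The last column is 4·(1.96 + 0.8416)²/(ln HR)². For a hazard ratio of 1.5 it exceeds the number of women in the trial. Placing 0.10 in the harm tail raises power at 1.5 only to 25%–48%.

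**5. Size of harm implied by the protocol's own figures.** Suppose the association in Section 1.2 were fully causal, with hazard 0.6 for women with arthralgia relative to 1 for those without. Averaging hazards over the rates in Section 13.2:

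(0.19·0.6 + 0.81) / (0.33·0.6 + 0.67) = 0.924 / 0.868 = 1.06.

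Abolishing arthralgia altogether on high dose would give 1/0.868 = 1.15. Detecting 1.06 with 80% power at two-sided 0.05 needs about 8,000 events.

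**The case against.** The strongest reply has four parts.

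- **Scope.** The sentence closes the primary-endpoint section, and Section 13.6 is silent, so a one-sided recurrence test is inferred rather than stated there. That is fair. However, the sentence says all tests and directly follows exploratory regressions, so it already reaches beyond the primary comparison, and nothing limits it.
- **Visibility.** A reader might infer that an excess would go unseen. The documents do not support that: Kaplan-Meier analysis by arm is planned and would show it descriptively. What is missing is a formal result and an interval.
- **Effect size.** A reader might invert the cited 40% reduction (1/0.6 = 1.67) and treat it as the harm to expect between arms. That would require every standard-dose woman and no high-dose woman to have arthralgia. With 33% and 19%, the figure is 1.06. The underlying analysis is also retrospective and covers tamoxifen as well as AI users, one trial did not confirm it, and Section 1.4 points the other way. Few events limit detection of harm more than sidedness does.
- **Other analyses.** A reader might infer that one-sided testing is undefined throughout the secondary and exploratory analyses. It is not. Objectives 2.2.1 and 2.2.2 are directional, and Section 1.2 gives a direction for grip strength, BMI, prior hormone replacement and chemotherapy. Only age, race/ethnicity and taxane use lack one, and they are adjustment variables.

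These points reduce the stakes. They do not make a benefit-only test appropriate for recurrence.

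**Conclusion.** The point holds in a limited form. As written, the plan's only between-arm recurrence comparison is one-sided at 0.10 toward benefit and cannot formally declare an excess on high dose, although the protocol's background gives a hedged reason to consider both directions. This is a reporting weakness in an exploratory endpoint. It does not affect the primary result, the sample size or the futility rule.

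Two-sided reporting would not make the trial able to rule harm in or out: with 10 to 30 recurrences the interval spans a factor of 3.5 to 2.0 each way. Its value is that it shows this uncertainty. The event counts and the hazard ratios of 1.5 and 2.0 are assumptions. The 1.06 rests on the plan's arthralgia rates and on a fully causal reading of one retrospective association.

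**What to change.** - In Section 13.4, confine the one-sided alpha of 0.10 to the week-12 primary comparison and the interim futility look that uses it.
- In Section 13.6, state that recurrence will be reported as a hazard ratio with a two-sided 95% confidence interval and a two-sided log-rank p-value, alongside the Kaplan-Meier curves, labelled exploratory and underpowered.
- Report adjustment covariates that carry no stated hypothesis with two-sided intervals.

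For the directional secondary objectives a one-sided test is defensible; bringing them under the narrower rule is for consistency.

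The cost is a wording change, best made before recurrence is compared by arm. Exploratory p-values become slightly less favourable. No visit, data item, sample size or primary analysis changes.

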13.7 Futility Analysis

One interim analysis will be added to the study. It is expected to take place half-way through the study after 46 patients in each of the treatment group are enrolled and evaluable for the primary endpoint. The purpose of the interim analysis is to allow the study to stop early for lack of efficacy (futility). A non-binding O’Brien-Fleming spending function is used to calculate the futility boundary. Calculations were performed using nQuery Advisor + nTerim 3.0 (Statistical Solutions. Boston, MA).

The following table summarizes the futility boundary at each analysis when 50% and 100% patients are enrolled and evaluable at the interim analysis and the final analysis. The futility boundary in the term of p-value scale at the interim analysis is calculated as $p=0.47$ (or $Z=0.076$). If the one-tailed p-value exceeds 0.47, it will be recommended that the trial stop for futility.

Looks	Information	n per group	Futility Boundary (Z value)	Futility Boundary (one-tailed p value)
1	50%	46	0.076	0.47
2	100%	93	1.28	0.05

In order to preserve power and compensate for the interim futility analysis which tends to reduce power, the sample size of the study is increased from 88 per group to 93 per group, which is 196 total if considering a 5% drop out rate.

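### The final-look row of the futility table pairs Z = 1.28 with a one-tailed p of 0.05; Z = 1.28 is p = 0.10, so the plan carries two thresholds for the primary endpoint

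*Combined protocol and SAP*

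**What the plan says.** Section 13.2 sizes the trial with these words: "Assuming a one-sided test with $\alpha=0.10$, $\beta=0.20". The assumed AIA rates are "33% of women on standard dose of vitamin D, and 19% of women on a high dose of vitamin D, developed AIA". Section 13.4 names the primary test, "Group differences in AIA rate will be assessed using the Chi-square test", and fixes its level: "All statistical tests are one-sided with $\alpha = 0.10$ as the level of significance".

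Section 13.7 adds one non-binding futility look at half the information, with an O'Brien-Fleming spending function, and says that "the sample size of the study is increased from 88 per group to 93 per group". Its table gives each look's boundary twice, once as a Z value and once as a one-tailed p value. Look 1 (46 per group) has Z = 0.076 and p = 0.47. Look 2 reads "2 100% 93 1.28 0.05", that is Z = 1.28 and p = 0.05.

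**The concern.** The two boundary columns should be the same threshold on two scales. They are at look 1 and are not at look 2. The row therefore contradicts itself, and its p value contradicts the one-sided 0.10 stated in sections 13.2 and 13.4.

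The columns are labelled as futility boundaries, but at the final look there is no third outcome: a result that does not reach the boundary is a non-positive trial. The cell therefore bears on the decision for the primary endpoint. If the final one-sided p lies between 0.05 and 0.10, section 13.4 and the table's Z call the trial positive and the table's p does not. If that is settled only after the data are seen, either choice can be criticised as data-driven.

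The choice of test adds a smaller risk. The usual Pearson chi-square p value is two-sided. Comparing it directly with 0.10 amounts to requiring |Z| > 1.645, which is the threshold implied by the erroneous cell, so a reader could take the cell as confirming that practice.

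**Working it through.** **Inputs.** Rates 33% and 19%, one-sided alpha 0.10 and beta 0.20 (section 13.2); 1:1 allocation (section 3); chi-square test (section 13.4); 88 and 93 per group, looks at 46 and 93 per group, and the two boundary rows (section 13.7).

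**1. The table's own conversion, p = 1 − Φ(Z).**

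| Look | Z | p stated | 1 − Φ(Z) |
|---|---|---|---|
| 1 | 0.076 | 0.47 | 0.4697 |
| 2 | 1.28 | 0.05 | 0.1003 |

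Look 1 reproduces and look 2 does not. A two-tailed reading of 1.28 gives 0.2005, so that does not rescue the 0.05. A one-tailed p of 0.05 corresponds to Z = 1.645.

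**2. Which entry is wrong: the fixed-design sample size.**

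n = [z_α √(2p̄q̄) + z_β √(p₁q₁ + p₂q₂)]² / (p₁ − p₂)²

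Here p̄ = 0.26, 2p̄q̄ = 0.3848 (root 0.6203), p₁q₁ + p₂q₂ = 0.2211 + 0.1539 = 0.3750 (root 0.6124), and (p₁ − p₂)² = 0.0196.

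- Alpha 0.10: (1.2816 × 0.6203 + 0.8416 × 0.6124)² / 0.0196 = 1.3104² / 0.0196 = 87.6, so 88. This is the plan's figure.
- Alpha 0.05: (1.6449 × 0.6203 + 0.8416 × 0.6124)² / 0.0196 = 1.5357² / 0.0196 = 120.3, so 121.

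**3. Which entry is wrong: the interim boundary and the inflation.** With O'Brien-Fleming-type beta spending, the beta spent at half information is 2[1 − Φ(1.2816/√0.5)] = 0.0699. The drift is then solved so that total beta is 0.20 with a non-binding rule.

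| One-sided alpha | Drift | Interim Z (p) | Final Z | Inflation |
|---|---|---|---|---|
| 0.10 | 2.196 | 0.0763 (0.4696) | 1.2816 | 1.0695 |
| 0.05 | 2.559 | 0.333 (0.37) | 1.645 | 1.0592 |

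At alpha 0.10 the interim boundary matches the plan's 0.076 and 0.47. The inflation gives 86.25 × 1.0695 = 92.2, so 93, with the unpooled variance, or 88 × 1.0695 = 94.1 with the pooled one. That is consistent with the plan's 93. At alpha 0.05 the size would be 121 × 1.0592 = 128.2 per group. The design was therefore computed at one-sided 0.10, and the 0.05 is the odd entry.

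**4. What separates the two thresholds.** Exact two-stage binomial enumeration: 46 then 93 evaluable per arm, stop at the interim if Z < 0.076, uncorrected pooled Z.

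| Final rule | Power at 33% vs 19% | One-sided type I error, futility stop ignored |
|---|---|---|
| Z ≥ 1.28 (p ≤ 0.10) | 0.7999 | 0.097 to 0.102 |
| Z ≥ 1.645 (p ≤ 0.05) | 0.6993 | 0.051 |

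The difference in power is 0.7999 − 0.6993 = 0.1006.

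**5. An illustrative result in the gap.** Suppose 31/93 on standard dose and 22/93 on high dose develop AIA. The pooled rate is 53/186 = 0.2849, the standard error is √(0.2849 × 0.7151 × 2/93) = 0.0662, and Z = (9/93)/0.0662 = 1.46, one-sided p = 0.072. Section 13.4 calls this significant; the p column of the table does not.

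**The case against.** The strongest reply is that the plan states one significance rule, one-sided 0.10, and states it twice. Section 13.4 governs the primary test. The table is about futility, its rule is non-binding, and nothing in the text says that success requires p below 0.05. The 0.05 is contradicted by the Z beside it and by every design figure, so it reads as a typing error that a careful statistician would override. On this view the 10-point loss of power is not built into the plan; it arises only if someone applies the wrong cell. Section 13.4 also says that all tests are one-sided, so comparing a two-sided chi-square p with 0.10 would disregard stated text.

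Much of this stands. The error looks isolated, the right value can be recovered from the plan, and the loss of power is conditional on the wrong cell being used. The chi-square sentence is a clarification, not a second error. What does not stand is that the cell is harmless. It is in the only table that gives the final boundary, and that boundary separates a positive from a non-positive primary result.

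The absolute powers can also be questioned, because they assume complete data on 93 per arm. Section 12.1.2 counts women who start treatment but miss the week 12 questionnaire as having AIA. Applying the 5% dropout of section 13.2 that way to both arms gives rates of 0.95 × 0.33 + 0.05 = 36.35% and 0.95 × 0.19 + 0.05 = 23.05%, and power of about 73.8% and 62.5%. That lowers both figures but leaves a gap of about 11 points.

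**Conclusion.** The concern holds. The look 2 p value in section 13.7 is wrong as written: Z = 1.28 is a one-tailed p of 0.10, and 0.10 is the level on which the rest of the design rests. Left in place, the cell gives the primary endpoint a second, stricter threshold.

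The two rules differ by about 10 points of power (80.0% against 69.9%) and by a factor of about two in one-sided type I error (about 0.10 against 0.051). These powers assume true rates of 33% and 19%, 93 evaluable women per arm, an interim at 46 per arm with the futility rule followed, and an uncorrected chi-square. The size of the gap depends little on the dropout assumption; the inconsistency in the table depends on none of these assumptions. It should be corrected before the final analysis.

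**What to change.** In the look 2 row of the section 13.7 table, change the one-tailed p from 0.05 to 0.10.

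As a clarification in section 13.4, say how the one-sided result is obtained: take Z as the signed square root of the uncorrected chi-square, positive when AIA is less frequent on high dose, and declare success if Z ≥ 1.28. The one-sided p is half the chi-square p when the difference is in that direction. The uncorrected form agrees with the 88 per group; a continuity-corrected calculation at the same inputs gives 102.

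The cost is one table cell and one sentence. Sample size, interim rule and data collection are unchanged.
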